# 8.1. Primary Efficacy Analysis

This protocol does not define any primary immunogenicity objectives or outcome measures.

# 8.2. Secondary Efficacy Analyses

TNA ED50, TNA NF50, and anti-PA IgG assay results will be presented for both the mITT and PP populations, providing a comparison of the sensitivity of immunogenicity results to subject adherence to protocol-defined conditions. The secondary immunogenicity endpoints of GMT/GMC, percentage of subjects achieving seroconversion, and percentage of subjects achieving putative seroprotection will be summarized as described above. These descriptive summaries are presented in Table 21, Table 22, Table 25, Table 26, Table 29 and Table 30.

Reverse cumulative distribution (RCD) curves will be presented for each assay (TNA ED50, TNA NF50, and anti-PA IgG), generated with separate panels for each visit and separate curves within each panel for each study arm. RCD curves are presented in Figure 3, Figure 4, Figure 5, Figure 6, Figure 7 and Figure 8.

Figures depicting the GMT (TNA ED50 and TNA NF50) or GMC (anti-PA IgG) for each assay over time will be presented by study arm in Figure 9, Figure 10, Figure 11, Figure 12, Figure 13 and Figure 14. Exploratory Efficacy Analyses

This protocol does not define any exploratory immunogenicity objectives or outcome measures. However, as enrollment for this study was stratified by sex and age category, secondary immunogenicity endpoint summaries will be stratified by sex and age category as exploratory analyses. TNA ED50 and NF50 and anti-PA IgG antibody responses will be summarized, stratified by sex and age category (18-30 years, 31-45 years), in Table 23, Table 24, Table 27, Table 28, Table 31 and Table 32.

# 9. SAFETY EVALUATION

All summaries and analysis of safety data will be presented for the safety population. Safety summaries will be presented overall and grouped by study arm.

Listings will be sorted by study arm, subject ID, parameter (if applicable), and visit.

Continuous variables will be summarized using the following descriptive statistics: n (non-missing sample size), mean, standard deviation, median, maximum, and minimum. All categorical measures will be summarized by the frequency and percentages of observed levels will be reported for all categorical measures. The denominator for the percentages may be based on the number of non-missing observations for an assessment or based on the number of subjects in a population. This will be described for each table.

# 9.1. Demographic and Other Baseline Characteristics

Summaries of age, sex, ethnicity, and race will be presented by treatment group overall and by group for all enrolled subjects (Table 18 and Table 19). Ethnicity is categorized as Hispanic or Latino, or not Hispanic and not Latino. In accordance with NIH reporting policy, subjects may self-designate as belonging to more than one race or may refuse to identify a race, the latter reflected in the CRF as "No" to each racial option.

Individual subject listings will be presented for all demographics (Listing 6).

#### 9.1.1. Prior and Concurrent Medical Conditions

All current illnesses and past or pre-existing medical conditions will be coded using Medical Dictionary for Regulatory Activities (MedDRA®) version 25.1 or higher.

Summaries of subjects' prior and concurrent medical conditions will be presented by study arm (Table 20).

Individual subject listings will be presented for all reported medical history including prior and concurrent medical conditions (Listing 7).

#### 9.1.2. Prior and Concomitant Medications

Prior and concomitant medications will be coded to the Anatomical Therapeutic Chemical (ATC) classification system as defined by the WHO Drug Dictionary. Summaries of medications that were started prior to dosing and continuing at the time of dosing will be presented by ATC levels 1 and 2 and study arm for subjects in the safety population (Table 86).

Individual subject listings will be presented for all concomitant medications (Listing 18).

# 9.2. Measurements of Treatment Compliance

All subjects are to receive 2 study vaccinations administered in the clinic. The number of subjects receiving study vaccination by week will be presented by study arm in Table 15 and Table 16 and as part of the subject disposition table (Table 13). Listing 1 presents subjects who received investigational product with randomized study arm and study product received for each study vaccination. Listing 8 presents subjects who missed doses of study vaccine or received study vaccine out of window.

# 9.3. Adverse Events

A summary of all adverse events is provided in Table 33. A summary of those events that occurred in  $\geq$ 5% of subjects in any study group is provided in Table 34.

#### 9.3.1. Solicited Events and Symptoms

Systemic solicited adverse events were collected pre-vaccination, and systemic and local solicited adverse events were collected 30 minutes post-vaccination and then daily for 7 days after each vaccination and graded on a scale of 0 (absent), 1 (mild), 2 (moderate) and 3 (severe). Systemic events include fever, feverishness, fatigue, malaise, myalgia, arthralgia, headache, and nausea, with grading scales as defined in Table 8; the quantitative grading scale for fever is included in Table 9. Injection site events include pain, tenderness, pruritus, ecchymosis, erythema/redness, and edema/induration with grading scales as defined in Table 6. Ecchymosis, erythema/redness, and edema/induration are measured by both functional and measurement grading scales as defined in Table 7.

The number and percentage of subjects reporting at least one solicited adverse event will be summarized for each solicited adverse event, any systemic symptom, any local symptom, and any symptoms. Corresponding 95% CIs will be calculated using Clopper-Pearson methodology from a binomial distribution (SAS Proc Freq with a binomial option). Solicited events occurring post first vaccination will be presented in Table 35, post second vaccination in Table 36, and post any vaccination in Table 37. Summaries of solicited events following any vaccination will be stratified by sex in Table 38 and stratified by age category in Table 39.

For each systemic and local event, any systemic event, any local event, and any solicited event, the maximum severity over 7 days after each vaccination will be summarized for the safety population. The number and percentage of subjects reporting each event will be summarized by the maximum severity and study arm, separately for each vaccination and over all vaccinations (Table 40, Table 41 and Table 42).

The number of subjects reporting a solicited adverse event will be summarized for each day post vaccination for each vaccination and for all vaccinations combined both in tabular form (Table 43, Table 44, Table 45 and Table 46) and graphically in bar charts (Figure 15 and Figure 16). A comparison of the event rate for each study arm between vaccination 1 and vaccination 2 will be presented in Table 47.

Solicited adverse events by subject will be presented in Listing 10 and Listing 11.

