Height and weight will be collected at the screening visit for calculation of the BMI. Vital signs (oral temperature, pulse, and blood pressure) will be collected at the screening visit and prior to each study vaccination. Vital signs assessed on Day 1 prior to the first study vaccination will be considered as baseline. Participants must not eat or drink anything hot or cold, or smoke within 10 minutes prior to taking an oral temperature. A 12-lead electrocardiogram will be performed at screening and reviewed by an investigator and designated cardiologist.

Reactogenicity assessments will include an assessment of solicited AEs occurring for the week after each study vaccination (Days 1 through 8 and target of Days 15 through 22, inclusive), which includes an assessment of injection site reactions including pruritus, ecchymosis,

erythema, edema/induration, pain, and tenderness as well as systemic reactions including fever, feverishness, fatigue, malaise, myalgia (exclusive of the injection site muscle pain), arthralgia, headache, and nausea. If a reactogenicity event persists on Day 8 or 22 (or the last day of the second reactogenicity period, should the second vaccination occur after Day 15), it will be followed until resolution. Pre-administration reactogenicity assessments will be performed immediately prior to each study vaccination to establish baseline.

Participants will be observed in the clinic for at least 30 minutes after each study vaccination. The study vaccination site will be examined, post-administration reactogenicity assessments will be performed, and any AE/SAEs will be recorded on the appropriate eCRF prior to discharge from the clinic. The study vaccination site will also be examined on approximately Day 8 after the first vaccination and Day 22 after the second (or the last day of the second reactogenicity period, should the second vaccination occur after Day 15).

All participants will complete a memory aid using an eMemory Aid from the time of first study vaccination through Day 8 and the second vaccination through Day 22 (or the last day of the second reactogenicity period, should the second vaccination occur after Day 15). Memory aids will be completed online and reviewed by the study staff.

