- Participants will be randomized in Advantage eClinicalSM and randomly assigned to a treatment arm prior to study vaccination.
- Pre-administration reactogenicity assessments will be performed immediately prior to study vaccination to establish baseline.
- Participants will then receive one dose of study vaccine via a single IM injection into the
  deltoid muscle of the participant's preferred arm. The site of injection (right or left arm)
  and time of study vaccine administration will be recorded on the appropriate eCRF.
   Participants will be observed in the clinic for at least 30 minutes after study vaccination.
  The study vaccination site will be examined, post-administration reactogenicity
  assessments will be performed, and any AE/SAEs will be recorded on the appropriate
  eCRF prior to discharge from the clinic.
- Participants will be trained to complete a web based "eMemory Aid" and are expected to enter information in the eMemory Aid each day. Participants using the eMemory Aid will also be provided a paper memory aid for their use in the event they are unable to access the web-based system. The participants will be asked to enter the information from the paper memory aid into the eMemory Aid once they are able to access the web-based system. Participants will be provided with instructions on completion of the electronic memory aid and other study-related materials. They will learn to record daily oral temperature, solicited injection site and systemic reactions, unsolicited AEs, and concomitant medications. Participants will be encouraged to take their oral temperature around the same time each day. They must not eat or drink anything hot or cold, or smoke within 10 minutes prior to taking their oral temperature. Participants will be

instructed on how to use their memory aid and how to measure and record AEs prior to discharge from the clinic. They will be instructed to notify the study center if they develop any severe reactions after study vaccination. If the site PI or appropriate sub-investigator deems the reaction severe enough, further instructions will be given to the participant on the proper course of action, including a return to the clinic for immediate evaluation if appropriate.

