## 9.2 Methods and Timing for Assessing, Recording, and Analyzing Safety Parameters

#### 9.2.1 Adverse Events

**Adverse Event (AE):** ICH E6 (R2) GCP defines an AE as any untoward medical occurrence in a patient or clinical investigation participant administered a pharmaceutical product and which does not necessarily have a causal relationship with this treatment. The FDA defines an AE as any untoward medical occurrence associated with the use of a drug in humans, whether or not considered drug related.

An AE can therefore be any unfavorable and unintended sign (including an abnormal laboratory finding), symptom, or disease temporally associated with the use of a medicinal (investigational) product. The occurrence of an AE may come to the attention of study personnel during study visits and interviews of a study recipient presenting for medical care, or upon review by a study monitor.

AEs, including solicited injection site and systemic (subjective and quantitative) reactions, not meeting the protocol-defined criteria for SAEs, will be recorded on the appropriate eCRF. Information to be collected for unsolicited non-serious AEs includes event description, date of onset, licensed study physician's assessment of severity and relationship to study product or alternate etiology (if not related to study product) (assessed only by those with the training and authority to make a diagnosis and listed on the Form FDA 1572 as the site PI or sub-investigator), date of resolution, seriousness, and outcome. AEs occurring during the trial-collection and reporting period will be documented appropriately regardless of relationship to study product. AEs will be followed through resolution.

Any medical condition that is present at the time that the participant is screened will be considered as baseline and not reported as an AE. However, if the severity of any pre-existing medical condition increases, it will be recorded as an AE.

AEs must be assessed for severity and relationship to study product (see definitions below). AEs characterized as intermittent require documentation of onset and duration of each episode. The start and stop date of each reported AE will be recorded on the appropriate eCRF.

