### Table 38:Number and Percentage of Subjects Experiencing Solicited Events Post Any Vaccination by Symptom, Study Arm, and Sex - Safety
Population (continued)

	Liquid AV7909 (N=X)				Lyophilized AV7909 (N=X)				All Subjects (N=X)			
	Fen	nale Male Female Ma			ale	Female		Male				
Symptom	n	%	n	n %		%	n	%	n	%	n	%
Edema/Induration												
Edema/Induration (measurement)												
Notes: N = Number of subjects in the safet a Exact binomial confidence interval calcul	Addition (measurement)       Image: Inditiation (measurement)         Jotes: N = Number of subjects in the safety population who received the first study vaccination; n = Number of subjects with reported event.         Exact binomial confidence interval calculated using Clopper-Pearson methodology.										•	

Tables with similar format:

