#### Table 43: Number and Percentage of Subjects Experiencing Solicited Events by Symptom, Severity, and Day Post First Vaccination - Liquid AV7909, Safety Population (continued)

Severity is the maximum severity reported post dosing for each subject for each day.

Tables with similar format:

- Table 44:Number and Percentage of Subjects Experiencing Solicited Events by Symptom, Severity, and Day Post First Vaccination -
Lyophilized AV7909, Safety Population
- Table 45:Number and Percentage of Subjects Experiencing Solicited Events by Symptom, Severity, and Day Post Second Vaccination -
Liquid AV7909, Safety Population

[Implementation Note: Update N footnote to "...who received the second study vaccination"]

Table 46:Number and Percentage of Subjects Experiencing Solicited Events by Symptom, Severity, and Day Post Second Vaccination -
Lyophilized AV7909, Safety Population

[Implementation Note: Update N footnote to "...who received the second study vaccination"]

Study Arm		Dose 2 - No Symptoms	Dose 2 - Mild or Greater Symptoms	Dose 2 - Total
		n (%)	n (%)	n (%)
		Systemic Symptoms		
Liquid AV7909	Dose 1 - No Symptoms	x (%)	x (%)	x (%)
(N=X)	Dose 1 - Mild or Greater Symptoms	x (%)	x (%)	x (%)
	Dose 1 - Total	x (%)	x (%)	x (100%)
Lyophilized AV7909	Dose 1 - No Symptoms	x (%)	x (%)	x (%)
(N=X)	Dose 1 - Mild or Greater Symptoms	x (%)	x (%)	x (%)
	Dose 1 - Total	x (%)	x (%)	x (100%)
		Injection Site Sympto	ms	
Liquid AV7909	Dose 1 - No Symptoms	x (%)	x (%)	x (%)
(N=X)	Dose 1 - Mild or Greater Symptoms	x (%)	x (%)	x (%)
	Dose 1 - Total	x (%)	x (%)	x (100%)
Lyophilized AV7909	Dose 1 - No Symptoms	x (%)	x (%)	x (%)
(N=X)	Dose 1 - Mild or Greater Symptoms	x (%)	x (%)	x (%)
	Dose 1 - Total	x (%)	x (%)	x (100%)
Notes: N = Number of s Denominators for perce	subjects in the safety population; $n = Numl$ ntages are the number of subjects in the sa	per of subjects with reported event. fety population who received the fi	rst and second dose of study vaccination.	

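### Solicited-event rates are not linked to the same dose's pre-dose grade, so unchanged pre-existing subjective systemic symptoms count as events; add a supporting new-or-worsened count

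*SAP*

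**What the plan says.** **Collection.** Protocol 7.1 states: "Pre-administration reactogenicity assessments will be performed immediately prior to each study vaccination to establish baseline". Protocol 8.1.2 and 8.2.2 repeat this for the Day 1 and Day 15 visits. SAP 9.3.1 confirms that "Systemic solicited adverse events were collected pre-vaccination".

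**Rates.** SAP 9.3.1 defines the summary in Tables 35-37 thus: "The number and percentage of subjects reporting at least one solicited adverse event will be summarized for each solicited adverse event". The footnotes to the table shells describe the numerator only as "n = Number of subjects with reported event".

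**Severity.** For Tables 40-42, "the maximum severity over 7 days after each vaccination will be summarized for the safety population". Protocol 11.6.2 likewise takes the worst response over follow-up and splits it into none versus any grade. Table 47 cross-classifies participants as having no symptoms or symptoms of mild or greater grade after dose 1 and after dose 2.

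**Where the pre-dose grade appears.** Tables 43-46 have a separate pre-dose column, while their footnote says "Severity is the maximum severity reported post dosing for each subject for each day". Listing 10 includes the baseline assessments by participant.

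**Baseline rules.** SAP 3.3 defines baseline only as the last value before the first vaccination. Protocol 9.2.1 treats a medical condition present at screening as baseline, and adds: "However, if the severity of any pre-existing medical condition increases, it will be recorded as an AE".

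**The concern.** The plan collects a baseline for each dose and then does not use it in any rate. A participant with mild fatigue before the injection and the same mild fatigue on Day 1 enters the numerator exactly as someone whose fatigue began after the injection. A systemic symptom left over from dose 1 and still present at Day 15 would also count as a dose 2 event in Tables 36, 41 and 47.

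The pre-dose column in Tables 43-46 does not resolve this. It shows how many participants had a symptom before dosing, but not whether they are the same people who report it afterwards. The number with a new or worse symptom requires within-participant linkage, and no planned table provides it.

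Occurrence of solicited events is the primary tolerability outcome. With 20 participants per arm, each one counted only because of an unchanged symptom adds 1/20 = 5 percentage points to a rate.

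**Working it through.** The documents give neither a solicited-event rate nor a pre-dose symptom prevalence, so there is no stated figure to reproduce. The check has two parts.

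**1. Is the pre-dose grade used in any summary?**

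| Output | What is counted | Linked to pre-dose grade? |
|---|---|---|
| Tables 35-37 (and 38-39 by sex and age) | participants with a reported post-dose event | no |
| Tables 40-42 | maximum grade in the 7 days after a dose | no |
| Table 47 | none versus mild or greater, dose 1 by dose 2 | no |
| Tables 43-46 | daily post-dose grade, with a separate pre-dose column | shown side by side, not linked |
| Listing 10 | individual grades, including baseline | by hand only |

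The situation can arise. Exclusion criterion 1 lets a participant be dosed with minor residual symptoms of a nearly resolved illness, subject to the investigator's judgement. Protocol 8.2.2 applies the eligibility criteria again before dose 2, with listed exceptions that leave this one in place.

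The issue is confined to the subjective systemic symptoms. SAP 9.3.1 mentions pre-vaccination collection for systemic events only, and the Table 43 shell marks fever as not applicable pre-dose.

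**2. How large could it be?**

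Inputs:
- n = 20 per arm (Protocol 11.4.3).
- b = share with a symptom before the dose that persists unchanged unless it worsens. Assumed 5%, 10% and 15%.
- r = share who would have a new or worse symptom after the dose in any case. Assumed 30% and 50%, and independent of b.

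Formulas:
- Planned rate = b + (1 − b)r
- Rate counting only new or worse symptoms = r
- Expected excess per arm = 20[b + (1 − b)r − r] = 20b(1 − r)

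| b | r | Planned rate | New-or-worse rate | Excess of 20 |
|---|---|---|---|---|
| 5% | 30% | 33.5% | 30% | 20 × 0.05 × 0.70 = 0.7 |
| 10% | 30% | 37.0% | 30% | 20 × 0.10 × 0.70 = 1.4 |
| 15% | 30% | 40.5% | 30% | 20 × 0.15 × 0.70 = 2.1 |
| 5% | 50% | 52.5% | 50% | 20 × 0.05 × 0.50 = 0.5 |
| 10% | 50% | 55.0% | 50% | 20 × 0.10 × 0.50 = 1.0 |
| 15% | 50% | 57.5% | 50% | 20 × 0.15 × 0.50 = 1.5 |

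The excess therefore runs from 0.5 to 2.1 participants of 20, or 2.5 to 10.5 percentage points.

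**Between arms.** If b is the same in both arms, the expected difference between arms is multiplied by (1 − b), that is 0.95, 0.90 or 0.85. It is slightly diluted and not shifted towards either arm. The chance that two arms with equal true rates differ by two or more participants, taking both counts as binomial with n = 20, is:

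| r | Planned count, b = 5%, 10%, 15% | New-or-worse count |
|---|---|---|
| 30% | 0.615, 0.623, 0.629 | 0.604 |
| 50% | 0.635, 0.634, 0.632 | 0.636 |

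Using the baseline hardly changes the chance imbalance. Ordinary binomial noise at this sample size accounts for nearly all of it.

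**The case against.** The strongest reply is that the SAP does what the protocol asks. The primary outcome is the occurrence of solicited events in the week after each dose, and Protocol 11.6.2 specifies the worst response, none versus any. Counting all reports is a legitimate definition and errs in the cautious direction for a phase 1 safety study. Replacing it would depart from the protocol's analysis of a primary outcome. It would also bring its own error: a mild headache that is present pre-dose, clears, and returns as mild on Day 3 would disappear, because a single pre-dose grade is set against a week's maximum. This stands, and it is why the main count should not be replaced.

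Part of the problem is also contained already. Residual symptoms are allowed at dosing only if they will not interfere with assessing systemic reactogenicity. Reactions ongoing at the Day 8 visit are recorded as AEs, and carry-over to dose 2 requires a symptom lasting about two weeks. With 40 participants, the linked count could be worked out from Listing 10. These points limit the size, but they do not put a new-or-worsened number into any table.

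A reader might infer three stronger things that the documents do not support.

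- **That the plan creates spurious gaps between arms.** At a pre-dose prevalence of 5%, 10% or 15%, the chance that the arms differ by two or more participants with pre-dose symptoms is 25%, 42% or 50%. That describes unequal pre-dose counts, not the planned comparison. It would carry over in full only if every such symptom persisted and none of those participants would have had a new or worse one. Randomisation and blinding balance background symptoms on average, and the study tests no formal hypothesis.
- **That the SAP breaks the worsening rule in Protocol 9.2.1.** That rule concerns medical conditions present at screening, not symptoms graded on the day of dosing. It is an analogy.
- **That these events are declared vaccine-caused.** The tables count solicited events and apply no causality filter.

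**Conclusion.** The point holds as a modest overstatement of absolute solicited systemic rates in both arms, arising because no summary links post-dose grades to the pre-dose grade for the same dose. Under the assumed ranges (pre-dose prevalence 5-15%, new-or-worse rate 30-50%, pre-dose symptoms otherwise persisting unchanged), the expected excess is about 0.5 to 2 of 20 participants per arm. Neither range comes from the documents, so this illustrates the scale and does not estimate it. No bias in favour of either formulation is expected. The main definition is defensible. What is missing is a sentence saying that it disregards the pre-dose grade, and a supporting count that uses the baseline already collected.

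**What to change.** 1. In SAP 9.3.1, keep the protocol-defined count as the main row and state that it includes all post-dose reports regardless of the pre-dose grade.
2. In Tables 35-37, 40-42 and 47, add a supporting row counting participants whose post-dose grade for a subjective systemic symptom (feverishness, fatigue, malaise, myalgia, arthralgia, headache, nausea) exceeds that symptom's pre-administration grade for the same dose. Leave fever out, because the Table 43 shell has no pre-dose entry for it.
3. State that the comparison for dose 2 uses the assessment made before dose 2, since SAP 3.3 defines baseline only relative to the first vaccination.

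The cost is SAP wording, one derived flag and one extra row per symptom, all from data already collected. A footnote should say that the supporting row may miss symptoms that resolve and recur at the same grade.
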